1. SYNOPSIS

Name of Sponsor/Company: Engage Therapeutics, Inc.	
Name of Investigational Product: Staccato Alprazolam (STAP-001)	
Name of Active Ingredient: alprazolam (8-Chloro-1-methyl-6-phenyl-4H-[1,2,4]triazolo[4,3-a][1,4]benzodiazepine)	
Title of Study: A Double-Blind, Placebo-Controlled, Inpatient, Dose-Ranging Efficacy Study of Staccato Alprazolam (STAP-001) in Subjects with Epilepsy with a Predictable Seizure Pattern	
Study center(s): Approximately 50 Study Sites with access to Clinical Research Unit (CRU) or Epilepsy Monitoring Unit (EMU) in the US, Canada, Australia and Jamaica	
Studied period (years): Estimated date first subject screened: March 2018 Estimated date last subject completed: August 2019	Phase of development: 2b
Objectives: The primary objectives are: 
 To assess the efficacy of STAP-001 in treating a seizure episode To assess the clinical feasibility and safety of the inhalation of STAP-001 in subjects during a seizure episode To assess the sedation associated with administration of STAP-001 	
Methodology: This is a multi-center, double-blind, randomized, parallel group, dose-ranging study to investigate the efficacy and clinical usability of STAP-001 in adult (18 years of age and older) subjects with epilepsy with a predictable seizure pattern. These subjects have an established diagnosis of focal or generalized epilepsy with a documented history of predictable seizure episodes as outlined in inclusion criterion #3. This is an in-patient study. The subjects will be admitted to a Clinical Research Unit (CRU) or Epilepsy Monitoring Unit (EMU) for study participation. The duration of the stay in the in-patient unit will be 2-8 days. One seizure event per subject will be treated with study medication. A treatable seizure event includes a predictable seizure episode, such that a change in the persistence of the seizure episode can be detected. The duration and timing of the seizure event and occurrence of subsequent seizures will be assessed by the Staff Caregiver(s) ¹ through clinical observation and confirmed with video electroencephalogram (EEG).	

¹ Staff member(s) assigned and trained to observe the subject throughout the entire Treatment Phase and facilitate the study drug administration as appropriate. Staff Caregivers will be accountable for the study medication and each handoff will be recorded.

The study consists of two parts: Part 1 Open-Label Feasibility; Part 2 - Double-Blind. Each part is divided into four phases: Screening; Qualification prior to entering the in-patient unit; Treatment in the in-patient unit; and Post-Treatment Safety Follow-Up. Subjects will provide appropriately-obtained informed consent or will have a legally authorized representative (LAR) sign the informed consent on his or her behalf prior to completing any study-related procedures.

The Screening Visit will involve the items identified in the Schedule of Events, including Informed Consent and distribution of the seizure diary. As part of the screening process the seizure events of the subjects must be confirmed as acceptable for continuation in the study by the Epilepsy Study Consortium Review Board. Eligible subjects will enter a Qualification phase during which the subject must have at least 4 or more predictable seizure episodes in a 28-day Qualification Period with no more than one week without a predictable episode. The Qualification Period may be extended beyond 28 days up to 56 total days to provide flexibility for scheduling of the Qualification Visit and Treatment Visit. The 28 days of the seizure diary activity immediately prior to the Qualification Visit will be assessed for qualification. At the end of the Qualification Period the Medical Monitor will review the seizure diary to confirm acceptable seizure frequency and subject's advancement into the Treatment Phase. Subjects meeting the qualification criteria will enter the CRU/EMU within 7 days from the end of the Qualification Period.

Part 1 Open-Label Feasibility

The first subjects enrolled in the study will participate in an open-label feasibility evaluation. Enrollment in this phase will end when there are data from at least eight individual subjects with a treated single seizure episode in a CRU/EMU. The subjects will be enrolled in 3-8 sites, up to three subjects per site. Eligible and qualified subjects will receive a single dose of 1 mg STAP-001 at the onset of their predictable seizure episode. The subjects will undergo all study procedures and evaluations as outlined in this protocol. The feasibility data (with special emphasis on the drug administration and clinical assessment procedures) from these eight subjects will be analyzed and reviewed by the Sponsor and study team before starting the double-blind part of the study. If deemed necessary based on the feasibility data, the study protocol will be amended (for example, to change the drug administration procedure or to redefine the time frame for primary endpoint assessment), before starting the double-blind part of the study.

Part 2: Double-Blind

After admission to the in-patient unit, eligible and qualified subjects will be randomly assigned (1:1:1) to one of two doses of STAP-001 (1 mg or 2 mg) or Staccato placebo. Randomization will be stratified by the use of inducing vs non-inducing AEDs and for use of chronic daily benzodiazepines (yes or no). For each subject, a single seizure episode will be treated and assessed. Study medication will be self-administered (when feasible) or administered by a Staff Caregiver when a predictable seizure episode starts. Assessment of the seizure activity is based on clinical observation by the Staff Caregiver using a stopwatch. In addition, a video EEG will record the occurrence, start time, and duration of the seizure event. Pharmacokinetic (PK) samples will be collected 10, 30 and 60 minutes, and 2 and 6 hours after the administration of the study drug. If possible, subjects will signal when they experience a seizure event. Subject will be under video EEG surveillance throughout the Treatment Phase. The Staff Caregiver will signal the event for the video EEG recording, start the stop watch at the time of drug

administration, and mark the occurrence of the seizure event on a seizure diary. If the seizure episode does not stop within 5 minutes of the study drug administration, rescue medication other than alprazolam may be administered at the discretion of the principal investigator per the protocol of the research unit. The study exit procedures will be conducted 24 to 32 hours after the administration of study medication or when the subject discontinues from the study.

After discharge from the in-patient unit there will be a safety-follow-up phone contact 14 days (± 2 days) after the subject received the study medication.

Number of subjects (planned):

Assuming a 10% drop-out/protocol violation rate, approximately 115 subjects will be randomized in the double-blind part of the study to provide approximately 35 evaluable subjects per treatment arm. Approximately 30% of the overall study population randomized in the study may be subjects being treated with chronic daily benzodiazepines as part of their epilepsy management. Approximately 9 subjects will be enrolled in the open-label feasibility part to provide 8 evaluable subjects. Approximately 50 trial sites will be recruited to conduct the study. The data base will be locked after the last subject included in the double-blind treatment period completes the study.

Diagnosis and main criteria for inclusion:

Subjects eligible for enrollment in the study must meet all of the following inclusion criteria and none of the exclusion criteria:

Inclusion Criteria:

1. Subject is able to provide, personally signed, and dated informed consent to participate in the study or will have a legally authorized representative (LAR) sign the informed consent on his or her behalf before completing any study related procedures.
2. Male or female ≥ 18 years of age.
3. Has an established diagnosis of focal or generalized epilepsy or focal and generalized epilepsy with a documented history of predictable seizure episodes that includes at least one of the following:
 - Generalized seizure episodes starting with a flurry of absence seizures or myoclonic seizures with a minimum duration of 5 minutes
 - Episodes of a prolonged focal seizure with a minimum duration of 3 minutes
 - Episodes of multiple (≥ 2) seizures within a 2-hour time period
4. Prior to randomization, has experienced ≥ 4 seizure episodes with predictable pattern during the last 4 weeks (qualification period) and no more than one week without a predictable seizure episode before entry into the in-patient unit.
5. Female participants (if of child-bearing potential and sexually active) and male participants (if sexually active with a partner of child-bearing potential) who agree to use a medically acceptable and effective birth control method throughout the study and for 1 week following the end of the study. Medically acceptable methods of contraception that may be used by the participant and/or his/her partner include abstinence, birth control pills or patches, diaphragm with spermicide,

intrauterine device (IUD), surgical sterilization, and progestin implant or injection. Prohibited methods include: the rhythm method, withdrawal, condoms alone, or diaphragm alone.

6. Subject is able to comply by the requirements of the protocol, particularly the requirements and specific Institution policies during the in-patient stay.

Exclusion Criteria:

1. History or diagnosis of non-epileptic seizures (e.g. metabolic or pseudo-seizures).
2. History of status epilepticus in the 6 months prior to Screening
3. Has a progressive neurological disorder such as brain tumor, demyelinating disease, or degenerative central nervous system (CNS) disease that is likely to progress in the next 3 months
4. Use of strong CYP 3A4 inhibitors; including azole antifungal agents (e.g., itraconazole, voriconazole), nefazodone, fluvoxamine, cimetidine, HIV protease inhibitors (e.g., zidovudine)
5. Has severe chronic cardio-respiratory disease
6. History of HIV-positivity.
7. Pregnant or breast-feeding.
8. Clinically significant renal or hepatic insufficiency (hepatic transaminases >2 times the upper limit of normal (ULN) or creatinine $\geq 1.5 \times$ ULN).
9. History of acute narrow angle glaucoma, Parkinson's disease, hydrocephalus, or history of significant head trauma.
10. Subjects who use medications to treat airways disease, such as asthma or COPD or have any acute respiratory signs/symptoms (e.g., wheezing).
11. Use of any investigational drug within 30 days or 5 half-lives of the investigational drug prior to administration of study medication, whichever is longer
12. A history within the past 1 year of drug or alcohol dependence or abuse.
13. Positive urine screen for drugs of abuse at Screening (positive Cannabis/Cannabinol results are acceptable if there is a documented history of stable use for medical purposes).
14. Known allergy or hypersensitivity to alprazolam.
15. History of glaucoma.
16. Subjects who currently have an active major psychiatric disorder where changes in pharmacotherapy are needed or anticipated during the study.
17. Hypotension (systolic blood pressure ≤ 90 mm Hg, diastolic blood pressure ≤ 50 mm Hg), or hypertension (systolic blood pressure ≥ 140 mm Hg, diastolic blood pressure ≥ 100 mm Hg) measured while seated at screening or baseline.
18. Significant hepatic, renal, gastroenterologic, cardiovascular (including ischemic heart disease and congestive heart failure), endocrine, neurologic or hematologic disease.

19. Subjects who, in the opinion of the Investigator, should not participate in the study for any reason, including if there is a question about the stability or capability of the subject to comply with the trial requirements.

Investigational product, dosage and mode of administration:

STAP-001 is a hand-held, single-dose, single-use drug-device combination product using the *Staccato* delivery system. Oral inhalation through the product initiates the controlled rapid heating of a thin film of excipient-free alprazolam to form a thermally generated, highly pure drug vapor. The vapor condenses into aerosol particles with a particle size distribution appropriate for efficient delivery to the deep lung. The rapid absorption of the drug provides peak plasma levels in the systemic circulation within minutes after administration.

Each product is packaged inside a sealed foil pouch. Removal of a pull-tab from the product renders it ready for use, as indicated by illumination of a green light. Successful dosing is signaled by the extinguishing of the green light.

Reference therapy, dosage and mode of administration:

Matching *Staccato* Placebo (exactly same inhalation device without coated alprazolam film)

Duration of treatment:

Subjects will receive a single dose of study medication.

Duration of study participation:

Subjects will participate in the study for up to 12 weeks, including Screening and Follow-Up. The Screening/Qualification Phase will last no more than 63 days. After that the subjects will participate in the Treatment Phase in the in-patient unit for approximately 2-8 days. Finally, there's a safety follow-up phone contact 14 days (± 2 days) after the subject received the study treatment.

Criteria for evaluation:

Efficacy:

The following will be assessed for every seizure episode and the 12-hour period following study medication administration:

Primary endpoint:

Proportion of responders in each treatment group achieving seizure activity cessation within 2 minutes after the administration of the study drug and no recurrence of seizure activity within 2 hours.

Secondary endpoints:

Seizure episode severity assessed by subject and/or Staff Caregiver

Use of rescue medication

Secondary generalization (evolution to a complex partial seizure and/or a generalized tonic-clonic seizure)

Exploratory endpoints:

Number of seizures during the 4, 6, and 12 hour time periods after study drug administration

Time to next seizure event with start time > 2 minutes after study drug administration

Pharmacokinetics:

Blood samples will be collected for plasma alprazolam concentration measurement pre-dose and at 10, 30, and 60 minutes, and 2 and 6 hours after the dosing of the study drug.

Safety:

Safety and tolerability of STAP-001 will be assessed by evaluating adverse events, vital signs, clinical laboratory and physical exams.

Sedation will also be assessed using a patient VAS.

Statistical methods:**Sample Size:**

There are no studies in the literature to provide reliable estimates of active treatment or placebo response rates. A total of 115 subjects will be enrolled in the double-blind part of the study to provide approximately 35 evaluable subjects per treatment arm [105 patients with approximately 30% of the overall study population randomized in the study being subjects with chronic daily benzodiazepines as part of their epilepsy management]. Power calculations assume a 2-sided test and significance level of 0.05 with 90% power and are based on the assumption that the proportion of responders with *STAP-001* is 57% (best active) whereas the assumed placebo responder rate is 20%.

Efficacy Analyses:

The efficacy population will include all subjects who have a seizure event and receive study drug during the double-blind Treatment Period. Data will be summarized by active treatment by dose level versus placebo-treated subjects (i.e., by treatment group). Continuous measures will be summarized descriptively (mean, standard deviation, median, minimum value, and maximum value) and categorical measures will be presented as number and percentage.

All statistical tests will be 2-sided with a significance value of 0.05. There will be no adjustments for multiple comparisons.

The primary efficacy analysis will be conducted following completion of the double-blind Treatment Period for the last subject. Additional details for statistical methods will be provided in the Statistical Analysis Plan.

Pharmacokinetic Analyses:

The PK population will include all patients who receive study drug and have at least one pharmacokinetic sample drawn and analyzed. Plasma concentrations will be summarized by descriptive statistics as appropriate and will be listed by patient.

Safety Analyses:

The safety population will include all subjects who receive study drug in the Treatment phase from both Part 1 and Part 2. Adverse events will be coded by system organ class (SOC) and preferred term with the Medical Dictionary for Regulatory Activities (MedDRA). Concomitant medications will be summarized by World Health Organization Drug Dictionary Anatomical-Therapeutic-Chemical (WHODrug-ATC) classification and preferred term. Adverse events (AEs), vital sign measurements, physical examination findings, electrocardiogram, clinical laboratory information, and concomitant medications will be tabulated and summarized by treatment and dose level. Separate tabulations will be produced for all treatment emergent AEs (TEAEs), TEAEs (by relationship to study drug), serious AEs (SAEs), discontinuations due to AEs or TEAEs, and AEs \geq Grade 3 severity. By-subject listings will be provided for any deaths, SAEs, and AEs leading to discontinuation of treatment.

Schedule of Events

	Qualification Phase			Treatment Phase	Exit Procedures ^a	Follow-up Phone Call
	Screen Visit	Qualification Period ^b	Qualification Visit			
Procedures	Day -35 (May extend to Day -63)	Day -35 to Day -8 (May extend to Day -63)	Day -7 to Day -1	Day 1 up to Day 8		14 ±2 days from Study Drug Administration
Informed consent	X					
Review of inclusion/exclusion criteria	X		X	X ^c		
Medical history	X			X ^c		
Physical examination	X			X ^c	X	
Neurological examination	X			X ^c	X	
Temperature (oral)	X			X ^c		
Height	X					
Weight	X			X ^c		
Respiratory rate and heart rate	X			X	X	
Blood pressure	X			X	X	
O ₂ saturation by pulse oximetry (SpO ₂)				X ^{de}		
Seizure Episode Severity Rating Scale				X ^f		
Sedation VAS				X ^g		
Dispense and begin Seizure Diary	X			X ^h		
Seizure Diary Completion		X		X		
Seizure Diary Collection and Review			X	X		
12-Lead ECG	X			X ^c	X	
Chemistry, hematology and urinalysis	X			X ^c	X	

^a 24 to 32 hours after the treatment administration for patients who received dosing; and at the time of exit for those who didn't seize.

^b During the Qualification Period the subject will record their seizure activity on the seizure diary. The Qualification Period may be extended beyond 28 days up to 56 total days to provide flexibility for scheduling of the Qualification Visit and Treatment Visit. The 28 days of the seizure diary activity immediately prior to the Qualification Visit will be assessed for qualification.

^c At Entry to CRU/EMU

^d At timepoint 0 (+2 min), and 10 (±2 min), 30(±2 min) and 60 (±5 min) minutes, 2 (±5 min) and 6 (±5 min) hours after the dosing of the study drug.

^e Attached at Entry into CRU/EMU

^f At timepoint 6 (±5 min) hours after the dosing of the study drug.

^g When multiple procedures are scheduled at the same time point, the VAS assessment should be performed first, immediately followed by the PK draw. Collected at timepoints 10 (±2 min), 30 (±2 min) and 60 (±5 min) minutes, 2 (±5 min) and 6 (±5 min) hours after the dosing of the study drug.

^h Staff Caregiver completes the seizure diary during the Treatment Phase

	Qualification Phase			Treatment Phase	Exit Procedures ^a	Follow-up Phone Call
	Screen Visit	Qualification Period ^b	Qualification Visit			
Procedures	Day -35 (May extend to Day -63)	Day -35 to Day -8 (May extend to Day -63)	Day -7 to Day -1	Day 1 up to Day 8		14 ±2 days from Study Drug Administration
Urine drug screen ⁱ	X			X ^c		
Urine Pregnancy test (if applicable)	X			X ^c		
PK Sample collection				X ^j		
Device training	X			X ^c		
EEG Recording				X ^k		
Study drug administration^l				X		
Adverse event assessment ^m	X	X	X	X	X	X
Subject seizure events forms sent to Epilepsy Study Consortium Review Board	X ⁿ					
Completed seizure diary sent to Medical Monitor for review			X			

ⁱ Drug Screen needs to be negative to allow entry into the CRU/EMU and dosing of the study drug.

^j PK sample will be collected at pre-dose (at time of admission to unit) and then at 10 (±2 min), 30 (±2 min) and 60 minutes (±5 min), 2 hours (±5 min) and 6 hours (±5 min) after the dosing of the study drug. If the PK sample is drawn outside of the timeframe, the sample will still be collected and evaluated.

^k Video EEG Recording will be throughout the subject's stay at the CRU/EMU

^l At the onset of the predictable seizure

^m Adverse Events will be collected throughout the study after Informed Consent is signed and through Follow-Up

ⁿ Forms completed and sent to review board within 48 hours after the subject or subject's LAR signs informed consent at the Screening Visit.

Schedule of Events – Procedures in CRU/EMU

	Entry to CRU/ EMU	Treatment Day: Schedule for day of Seizure Episode only						
		Time 0	10 min	30 min	1h	2 h	6 h	24h ^a / Exit Procedures
Medication history	X							
Review of eligibility criteria	X							
Physical Examination	X							X
Neurological Examination	X							X
Urine pregnancy test (if applicable)	X							
12-Lead ECG	X							X
Chemistry, hematology and urinalysis	X							X
Urine drug screen	X							
Weight	X							
Temperature (oral)	X							
Vital Signs (BP, HR, RR)	X		X ^e	X ^e	X ^f	X ^f	X ^f	X
Attach EEG electrodes	X							
Device training	X							
EEG Recording	X							X
Study Med administration		X ^{bcd}						
Start Stopwatch ^d		X						X
Insert Indwelling Catheter for PK samples	X							
PK Sampling	X		X ^e	X ^e	X ^f	X ^f	X ^f	
Sedation VAS ^g			X ^e	X ^e	X ^f	X ^f	X ^f	
Pulse Oximetry (SpO ₂) ^h		X ^e	X ^e	X ^e	X ^f	X ^f	X ^f	
Adverse Event Assessment ⁱ		X						X
Seizure Diary	X							X
Seizure Episode Severity Rating Scale							X ^f	

^a Patient can be discharged after 24 to 32 hr assessments at the discretion of the study staff

^b Time 0 is defined as the *start* of inhalation

^c Subjects should have minimal postural changes for the first 1.5 hours after administration of study drug

^d at seizure episode onset

^e ± 2 minutes

^f ± 5 minutes

^g When multiple procedures are scheduled at the same time point, the VAS assessment should be performed first, immediately followed by the PK draw.

^h Attached at Entry into CRU/EMU

ⁱ Post treatment

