11.1. Demographic Characteristics and Medical History

Demographic characteristics (i.e., gender, race and ethnic origin, date of birth, and calculated body mass index) will be collected at the Screening Visit, and detailed on the eCRF.

Thorough medical history, including EEG and brain imaging (MRI/CT) findings within the last 5 years, history of seizures, seizure pattern, frequency and characteristics during the last 12 months. Current medications, and co-morbidities will be collected at the Screening Visit and reviewed and updated at entry into the CRU/EMU for the Treatment Phase. Epilepsy history and seizure documentation are collated and submitted to the Epilepsy Study Consortium Review Board for review.

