13. STATISTICAL METHODS

13.1. Sample Size Rationale

There are no studies in the literature to provide reliable estimates of active treatment or placebo response rates for this study. Assuming a 10% drop-out/protocol violation rate, approximately 115 subjects will be enrolled in the double-blind part of the study to provide approximately 35 evaluable subjects per treatment arm. Enrollment may be stopped after 105 evaluable subjects have completed the study.

Approximately 30% of the overall study population randomized in the study may be subjects being treated with chronic daily benzodiazepines as part of their epilepsy management. Since the effect of concomitant chronic daily benzodiazepines use on study treatment is unknown, a 50% response rate for chronic benzodiazepines users on active treatment arms is assumed. For subjects who are not chronic benzodiazepines users, a response rate of 60% for active treatment arms is assumed. With up to 30% of study population being chronic benzodiazepines users and these response assumptions, a 57% response for the active treatment arm is targeted.

Power calculations assume a 2-sided test and significance level of 0.05 with 90% power and are based on the assumption that the proportion of responders with STAP-001 is 57% (best active treatment arm) whereas the assumed placebo responder rate is 20%.

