#### Primary Efficacy Endpoint

The primary efficacy endpoint will be the proportion of responders in each treatment group achieving seizure activity cessation within 2 minutes after the administration of the study drug and no recurrence of seizure activity within 2 hours. The primary endpoint will be analyzed with a chi-squared test. The overall treatment comparison, as well as pair-wise comparisons between each dose level and placebo will be performed. The estimates of the treatment difference versus placebo and their 95% confidence interval will be presented.

There will be no adjustment for multiple treatment group comparisons in this dose-ranging Phase 2b study. The dose-response relationship will be explored with a regression analysis.

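### Seizure pattern at entry is plausibly prognostic for the 2-minute/2-hour response, but neither it nor the two randomisation factors enters the primary test, so chance imbalance is uncorrected and a modest precision gain is forgone

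*Protocol*

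**What the plan says.** Protocol 8.1 and the Synopsis (inclusion criterion 3) require at least one of three documented patterns:

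- 3a: generalised episodes starting with a flurry of absence or myoclonic seizures, at least 5 minutes long.
- 3b: "Episodes of a prolonged focal seizure with a minimum duration of 3 minutes".
- 3c: "Episodes of multiple (≥ 2) seizures within a 2-hour time period", with no minimum duration.

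A subject may meet more than one. Protocol 11.1 has the site collect, at Screening, "history of seizures, seizure pattern, frequency and characteristics during the last 12 months", and the Epilepsy Study Consortium Review Board confirms that the subject's events are acceptable.

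One responder definition applies to everyone (Protocol 13.2.1; SAP 2.2.1 and 3.6): the treated seizure stops within 2 minutes of dosing and none recurs within 2 hours.

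Randomisation is stratified by inducing versus non-inducing AED and by chronic daily benzodiazepine use (Protocol 7.2), not by pattern. On the analysis, SAP 3.3.1 says "The primary endpoint will be analyzed with a chi-squared test", overall and for each dose against placebo, and Protocol 13.4.2 agrees. No strata or covariates are named. A regression is mentioned for dose-response, also without covariates. SAP 4.1.1 lists a descriptive seizure history table; SAP 4.1.2 lists no efficacy table by pattern.

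**The concern.** The endpoint asks different things of the three patterns. In 3a and 3b the documented episode outlasts the 2-minute window, so the main hurdle is early cessation. In 3c recurrence inside the 2-hour window is the defining feature and there is no duration floor, so the main hurdle is non-recurrence. Equal response rates over two different hurdles would be something of a coincidence.

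If pattern is prognostic, two things follow at 35 per arm. An arm that by chance has the more favourable mix has its observed response shifted, and the planned test does nothing about it. Variation between patterns also stays in the error term when a baseline variable could remove it. Both doses are compared with the same placebo arm and there is no multiplicity adjustment, so one unlucky placebo mix affects both comparisons.

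**Working it through.** **1. The plan's own figure.** Inputs from Protocol 13.1: "Power calculations assume a 2-sided test and significance level of 0.05 with 90% power"; 57% on the best active arm against 20% on placebo; a target of 35 evaluable per arm. With p̄ = (0.57 + 0.20)/2 = 0.385 and d = 0.37:

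n = [1.960·√(2·0.385·0.615) + 1.282·√(0.57·0.43 + 0.20·0.80)]² / 0.37² = (1.349 + 0.816)² / 0.1369 = 34.2, so 35 per arm.

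Power at 35 per arm is 90.7%, both by this formula and by exact enumeration of the uncorrected chi-squared test. Exact type I error at a common 20% rate is 4.9%. The stated design reproduces.

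**2. Size of a chance imbalance.** Assume a pattern with a 50% share and a 30-point difference in response between patterns; neither figure is in the documents. One SD of the between-arm difference in share is √(2·0.25/35) = 0.12. The shift in the observed effect is 0.12 × 30 = 3.6 points.

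For scale, the SE of the planned difference is √(0.4051/35) = 10.8 points, so this component is (3.6/10.8)² ≈ 11% of the variance. Across other assumed spreads, from 10/20/30% to 2/8/50% in equal shares, the SD of the shift is 2.0 to 5.1 points and the 95th percentile of its absolute size is 3.7 to 10 points. The planned difference is 37 points.

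**3. What an imbalance does when it occurs.** With a 50% share, a gap of 7 or more subjects (20 points) arises in 12% of single dose-placebo comparisons. It arises in 21% of trials for at least one dose. Given a 21 versus 14 split and no drug effect, the chance of a false positive favouring the better-mixed arm (nominal 2.5%) is:

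| Assumed rates in the two patterns | Chi-squared | CMH by pattern |
|---|---|---|
| 10% / 30% | 5.4% | 2.4–2.5% |
| 5% / 35% | 7.2% | 2.4–2.5% |

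The opposite imbalance would hide an effect.

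**4. Power with and without stratification.** Simulation with 35 per arm, pattern shares 20/40/40 (assumed), and a common odds ratio calibrated to 20% and 57% overall. The last column reassigns 30% of labels at random, so 0.30 × (1 − 0.04 − 0.16 − 0.16) = 19% are wrong (also assumed).

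| Placebo rates 3a/3b/3c | Chi-squared | CMH, accurate labels | CMH, 19% wrong labels |
|---|---|---|---|
| 20/20/20% | 90.8% | 90.0% | not tabulated |
| 12/16/27% | 90.6% | 90.6% | 90.4% |
| 7/12/34% | 90.9% | 93.1% | 91.6% |
| 3/9/40% | 90.8% | 95.9% | 93.0% |

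In the misclassified runs the chi-squared comparator was 90.8–90.9%. A separate set of scenarios agrees: a cost of 1.0 point with no spread, a gain of 0.7 at 10/20/30% in equal shares, and 3.8 at 5/15/40%. The most extreme case tried, 2/8/50%, gains about 7. Type I error is 4.8–4.9% for both tests in every scenario. These figures are for CMH on pattern alone; the further effect of adding the two randomisation factors was not quantified.

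**The case against.** The strongest case for the plan has four parts.

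- **No evidence of different rates.** Protocol 13.1 says there are no reliable response estimates at all, and none is given by pattern. Dosing is at onset. If each untreated episode ran its documented course, 3a and 3b would still be going at 2 minutes and 3c would recur within 2 hours, so all three would tend to fail. This stands: the definitions do not fix how far the rates differ, or which way. It does not remove the concern. The plan itself assumes 20% placebo response, so some episodes depart from their usual course, and nothing suggests they do so equally across patterns.
- **Randomisation already protects the test.** This stands on average over trials: type I error holds and chance imbalance is part of the standard error. It does not correct the one comparison actually observed, as step 3 shows.
- **Labels will be imprecise.** Patterns overlap, only one episode is treated, and no section says that a 3a/3b/3c code is recorded. This stands, and it reduces the gain to roughly 2 points or less in the scenarios tried.
- **The randomisation factors have the better claim to adjustment.** This also stands, and the fix includes them.

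A reader might infer that the trial is underpowered, or that the primary test is biased. The documents support neither. The 90% rests on overall rates and is met however the 20% is spread over patterns; power is forgone only relative to an adjusted test, and only if pattern matters.

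**Conclusion.** The point holds as a missed, inexpensive safeguard; it is not a flaw that invalidates the primary analysis. Pattern is plausibly prognostic, is collected before randomisation, and is used in neither randomisation nor analysis. The two factors that are used in randomisation are not carried into the test either.

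On assumed pattern rates and shares, adjusting for pattern is worth about 0 to 5 points of power with accurate labels, less with imprecise ones, and costs about 1 point if pattern does not matter. Its main value is protecting the realised dose-placebo comparisons against a chance difference in pattern mix. It would go too far to say that the patterns are known to have different response chances, or that the plan loses power against its own target.

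**What to change.** In SAP 3.3.1 and Protocol 13.4.2, with the change recorded in SAP 3.7 (now marked not applicable), pre-specify before unblinding:

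1. A covariate-adjusted comparison of each dose with placebo on the primary endpoint, with main effects for AED type, chronic benzodiazepine use and inclusion-3 pattern. Report the adjusted risk difference and its 95% CI.
2. A stated fallback for sparse cells: a CMH test on a single named factor. About 35 × 0.57 + 35 × 0.20 = 27 responders are expected per pairwise comparison, so crossing four randomisation strata with three patterns is not workable.
3. One pattern per subject, assigned from pre-randomisation screening data by a fixed rule, such as the predominant qualifying pattern, with a stated tie-break.
4. The unadjusted chi-squared test as a sensitivity analysis, and a responder table by pattern and arm.

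The cost is a change to the protocol's named primary test, one derived variable that may need to be coded from existing seizure history, and about 1 point of power if pattern is not prognostic. Sample size, randomisation and conduct do not change. The timing matters, because an adjustment chosen after an imbalance has been seen with treatment codes open would not be credible.
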